c.6.5. Research Protocol. The research assistant (RA) will explain the nature of the study, risks and benefits, the voluntary nature of participation, and the ability to discontinue participation at any time without consequences. After informed consent is obtained, participants will be randomized to the acupuncture or attention control group via a computer-generated random numbers table. Each number (1-26) and assigned group, will be written on an index card and placed in a sealed opaque envelope. The participants will select

one envelope from a sealed box. The participant, acupuncturist, and RA cannot be blinded to group assignment. All participants will complete two measures at baseline: the McGill Pain Questionnaire and the Seattle Angina Questionnaire-7.⁶⁹ Those in the treatment group will repeat the measures following all 10 acupuncture sessions. Those in the control group will repeat measures during weeks 1-5 after their attention control sessions. All participants will complete the AHA Angina Log throughout the study (weeks 1-5). Venipuncture will be performed at baseline and study completion for all participants.

c.6.6. Acupuncture Protocol. The acupuncturist will swab each point with alcohol. Needles will be inserted and retained for 30 minutes. Each needle will be rotated 3 times to stimulate the *qi* in the meridian 10 minutes after insertion, at 20 minutes after insertion, and just prior to removal at 30 minutes. Needles will be inserted using the standards of clean needle technique established by the Council of Colleges of Acupuncture and Oriental Medicine⁷⁰ One size acupuncture needle, 0.25 diameter × 40 mm length, will be used. All acupuncture needles are sterile, disposable, and made of surgical stainless steel with stainless steel wound heads. Sessions will be repeated twice weekly (with at least 2 off days in between) for 5 weeks (10 sessions).

c.6.7. Acupuncture Point Prescription for Chest Pain or Angina. The standardized point prescription uses acupuncture points on the front of the body to enable individuals, many who are acupuncture naïve, to remain supine. This is aimed at reducing anxiety by enabling the participant to anticipate needle insertions.

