c.6.8. Attention Control Health Videos Protocol. Individuals randomized to the attention control group will watch health videos on broad topics not containing content that could potentially improve pain. Videos will be viewed from weeks 1-5 (5 timepoints) and will equate to the time the experimental group receives acupuncture (~10 hrs.)⁷¹. Topics include *Defeating the superbugs; Can we live forever?; Do you see what I see?; Cracking your genetic code; How smart can we get?; Vaccines, calling the shots; Can I eat that?; and Alive inside (the benefits of music)*. The videos will be shown in the College of Nursing clinical laboratory room on the 4th floor. The standardized content has an additional benefit of assuring complete fidelity to the control protocol.

c.7.1. Measures.

c.7.1.a. Demographic Data Form (Appendix A). Personal characteristics will be assessed using the demographic data form. Standard measures including age, race/ethnicity, marital status, education, income, employment, and insurance are included.

c.7.1.b. Protocol Acceptability Scale for Treating Angina with Acupuncture (Appendix B). The Satisfaction instrument is a 10-item instrument used to measure acceptability of the study processes and protocols. Items are measured on a 0 (negative response, i.e. did not like acupuncture) to 2 (positive response) scale. The protocol will be deemed to have high acceptability and have an acceptability score > 10 (80%).

c.7.1.c. McGill Pain Questionnaire (MPQ) (Appendix C). The MPQ⁷² is a valid and reliable measure of pain.. The MPQ captures pain location and pain intensity on a 0 to 10 scale, where 0 is no pain and 10 is pain as bad as it can be and least and worst pain in the past 24 hours.

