c.7.1.g. **Biomarkers of Inflammation**. Proinflammatory cytokines IL-1 β , IL-2, IL-8, and IL-18; CRP^{76,77}; and TNF α , the anti-inflammatory cytokines IL-4, and IL-10,⁷⁶ and the dual pro/anti-inflammatory IL-6⁷⁸ will be measured to determine if there is a significant change baseline to post study (5 week). Venous blood (4.5 mls) will be collected in a blue-top tube containing 3.2% sodium citrate. Samples will be processed in our clinical lab in the college. Samples will be centrifuged at room temperature for 15 minutes; plasma will be removed into 2 cryovials in 1 ml aliquots and stored in a -80°C freezer immediately. A label with study ID number, date, and time of blood draw will be placed on the cryovials prior to freezing. Samples will be batch analyzed using high-sensitivity multiplex technologies.⁷⁹ See **Table 1** for all variables, measures, and data collection time points.

c.8. Potential Problems, Alternate Plans, and Limitations based on the Sample Proposed. Rigorous research into complementary and alternative therapies has been hindered by the inability to conduct placebo-controlled trials⁸⁰. Our attention control design is a strong alternative to an intervention that cannot be blinded to participant or interventionist without potential confounding treatment effects. Recruitment is always a potential problem with clinical research and we will enlist the help of the American Heart Association Chicago Affiliate and *WomenHeart* of Cook County to identify potential participants. Attrition is also a possible problem but [name] has experienced very little attrition in prior acupuncture studies. We will continue to enroll to retain 24 participants and we will address attrition with an intention to treat analysis. Design limitations were addressed in section c.3.

Table 1. Data Collection Variables, Measures, and Time Points (Both Groups)

Variable	Measure/Analyses	Data Collection Points (Baseline) (10 tx sessions) (5 wks.)		
Aim 1				
Recruitment	Number enrolled/number invited to participate	X		X
Retention	Number retained at study completion/number recruited	X		X
Completion	Number of time points completed/12 (total)	X		X
Acceptability	Protocol Acceptability Scale for Treating Angina with Acupuncture			X
Aim 2				
Effect Size	Intra-individual effect : mean pre-scores – mean post-scores/pooled s.d. Group effect : mean differences in scores between acupuncture and attention control group.	X		X

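### Table 1 scores Completion out of 12 for both groups, but 12 is the acupuncture schedule; the same count gives controls 7, and no control denominator is stated

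*Combined protocol and SAP*

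**What the plan says.** The combined protocol and SAP lists Completion among the Aim 1 measures in "Table 1. Data Collection Variables, Measures, and Time Points (Both Groups") and defines it as "Number of time points completed/12 (total"). No second denominator is given. The table's timing columns read "Data Collection Points (Baseline) (10 tx sessions) (5 wks".).

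The two arms follow different schedules. In c.6.5, "Those in the treatment group will repeat the measures following all 10 acupuncture sessions", and "Those in the control group will repeat measures during weeks 1-5 after their attention control sessions". Section c.6.8 gives the number of control sessions: "Videos will be viewed from weeks 1-5 (5 timepoints) and will equate to the time the experimental group receives acupuncture (~10 hrs".). Both arms have a baseline assessment and an end-of-study contact: "Venipuncture will be performed at baseline and study completion for all participants" (c.6.5). Section c.6.4 adds that data are collected on both sides of each session, without naming an arm.

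The Aim 1 hypothesis in c.9.1 sets 80% as the target for recruitment, retention and completion. No section defines a time point or says in which arm the completion target is judged.

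**The concern.** One fixed denominator is attached to two schedules of different length. The figure of 12 matches the acupuncture arm, and the table title extends it to the controls, who have half as many sessions. Scored that way, a control with perfect attendance would look like a poor completer, and the shortfall would come from the denominator and not from behaviour.

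Completion is one of three 80% targets in the Aim 1 hypothesis, and Aim 1 is there to inform the design of the R21 study. A low control figure could be misread as evidence that the attention-control schedule is hard to complete.

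**Working it through.** **Inputs**

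- Completion denominator: 12, in a table titled for both groups (Table 1).
- Points shared by the arms: baseline (c.6.5) and a 5-week point (Table 1 columns; the study-completion blood draw in c.6.5).
- Sessions followed by measures: 10 for acupuncture (c.6.4, c.6.5); 5 for controls (number from c.6.8, measures after sessions from c.6.5).
- Target: 80% (c.9.1).

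**Formula.** Scheduled points = a + k × s, where a is the number of non-session points, k the collections counted per session, and s the number of sessions.

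**Reproducing the plan's figure.** With a = 2 (baseline and a separate 5-week point) and k = 1, acupuncture gives 2 + 1 × 10 = 12, an exact match.

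**The same rule for controls.** 2 + 1 × 5 = 7.

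**Other rules applied equally to both arms**

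| Rule | a | k | Acupuncture | Control |
|---|---|---|---|---|
| One point per session, separate 5-week point | 2 | 1 | 12 | 7 |
| One point per session, 5-week point coincides with last session | 1 | 1 | 11 | 6 |
| Before and after each session, separate 5-week point | 2 | 2 | 22 | 12 |

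In general the arms differ by (a + 10k) − (a + 5k) = 5k, which is above zero whenever sessions are counted at all. With a = 2, acupuncture reaches 12 only at k = 1 and controls only at k = 2. A rule that ignores sessions (k = 0) makes the arms equal but does not reach 12: baseline, 5-week point, five weekly log points and two blood draws, each counted separately, give 1 + 1 + 5 + 2 = 9.

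**Against the target.** 0.8 × 12 = 9.6, so 10 points are needed.

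- Separate 5-week point: a control with full attendance scores 7/12 = 58.3%; acupuncture can score 12/12 = 100%.
- 5-week point coinciding with the last session: control 6/12 = 50.0%; acupuncture 11/12 = 91.7%.

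Section c.9.1 does not say whether the 80% applies to each participant or to an average. It makes no difference here, because the mean over controls cannot exceed the maximum any one control can score.

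**With an arm-specific denominator.** A control with full attendance scores 7/7 = 100%. Since 0.8 × 7 = 5.6, the target would be met with 6 of 7 points.

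**The case against.** The strongest reply is that Completion was meant for the acupuncture arm. The hypothesis carrying the 80% speaks of acupuncture therapy, the middle timing column counts treatment sessions, and c.9.1 refers to adherence to the treatment schedule. Two other measures in the same table, the needling-sensation scale (c.7.1.f) and the acceptability scale (c.7.1.b), do not fit controls literally either, so the title is imperfect evidence of scope. On this reading 12 is correct and 80% is attainable. That much stands. But nothing limits Completion to one arm, Aim 1 is about study processes, and Recruitment and Retention in the same block count all participants. Even if the reply is right, completion of the control schedule has no definition in an attention-control pilot.

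Three stronger readings are tempting but not supported.

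- A reader might infer that no way of counting gives both arms 12. One does: acupuncture once per session (1 + 10 + 1) and controls before and after each session (1 + 2 × 5 + 1). The documents state no such mixed rule, and c.6.5 describes after-session measures in both arms. The claim therefore holds only for a rule applied equally.
- A reader might infer that the roughly 10 matched hours in c.6.8 prove the five control time points are not an error for ten. They do not: five sessions of 2 hours and ten of 1 hour give the same total. Five is used here because it is what c.6.8 states and no section gives controls ten sessions.
- A reader might infer that the trial as a whole must miss its 80% target. That requires pooling the arms, which the documents do not specify.

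It is also fair to say that the effect is limited. Retention is defined without reference to sessions and works in both arms.

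**Conclusion.** The point holds as a defect in one feasibility measure. The denominator of 12 reproduces the acupuncture schedule and does not fit the control schedule. Applied as the table title implies, it caps a fully attending control at 58.3% (50.0% if the 5-week point coincides with the last session) against a target of 80%. If it is meant for acupuncture only, the figure is right for that arm, but its scope is unstated and control completion is undefined.

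This rests on five control sessions as c.6.8 states, on one counting rule for both arms, and, for the 12 and 7, on a 5-week point separate from the last session, as the Table 1 columns suggest. Completion is summarised descriptively and has no go/no-go rule attached. No efficacy or safety result changes.

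**What to change.** In Table 1, define Completion as time points completed divided by time points scheduled for the participant's arm, and say what counts as one time point. On a visit count the denominators are 12 (acupuncture) and 7 (control) if the 5-week visit is separate, or 11 and 6 if it coincides with the last session; the plan should state which.

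In c.9.1, state that the 80% criterion applies to that ratio, that it is reported by arm, and in which arm or arms it is judged. If only the acupuncture arm is to be judged, say so and still report the control ratio descriptively.

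The cost is one line in Table 1 and one sentence in c.9.1, with no extra data.

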c.6.2. Power Analysis. This feasibility pilot study is not powered to detect significant effects for improvement in symptom outcome measures. However, In order to achieve 80% power to detect a large effect size using Cohen's classification ($EF=.80$), 52 patients randomized and completing the final symptoms assessments will be needed. Based on our sample of 26 participants, we will be able to detect a Cohen's d effect size of 1.10 as statistically significant. While a large effect size is not anticipated in this pilot feasibility study, an expanded trial will be adequately powered to explore the threshold for a clinically meaningful effect.

c.6.3. Retention Strategies. We anticipate an attrition rate of no more than 10%, which means we expect a 90% retention rate for the subjects. These numbers are based on accruals and withdrawals in [name] previous 10 session acupuncture trial for which there were 36 accruals and no withdrawals. The following retention strategies will be employed: Participants will be engaged as active partners in the research by addressing possible benefits of acupuncture (experimental group) and non-pain related health education (control group) as well as the importance of their contribution to science. Data collection will be scheduled at convenient times for participants, including weekend and evening appointments. Multiple contact information (e-mail, cell phone, and home phone) will be collected to improve adherence to appointments. We also will offer \$10 per visit to cover the cost of travel.

c.6.4. Procedures. The research assistant will screen and consent eligible individuals. The potential participants will be informed that they will either be randomized to the acupuncture group (10-acupuncture session protocol, two treatments per week for five weeks) or the attention control group. Data will be collected on tablet computers before and after each session. Control group members will be offered the acupuncture protocol at study completion.

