C.7.1.d. Seattle Angina Questionnaire-7 (SAQ-7) (Appendix D). The instrument consists of 7 items in 5 domains (Physical Limitation, Angina Stability, Angina Frequency, and Quality of Life) measuring the impact of angina on participants' health status. Item responses are coded sequentially from worst to best status and range from 1 to 6 except Quality of Life (range 1-5). Scores are generated for each domain and are scaled 0 to 100, with 0 denoting the worst and 100 the best possible status⁶⁹. The SAQ-7 was validated among patients presenting with stable IHD, undergoing percutaneous coronary intervention, and after acute myocardial infarction⁷³. High levels of concordance (0.88–1.00) with each original SAQ domain were found. The SAQ-7 demonstrated good construct validity (compared with Canadian Cardiovascular Society class for angina; $r=0.38-0.62$) for patients with stable CAD.⁶⁹

c.7.1.e. AHA Angina Log (Appendix E). *My Angina Log* is a simple 1 page log used to measure each episode of angina. Participants are instructed to record the date and number of times they experienced angina as well as triggers and treatments.⁷⁴ Severity of symptoms are measured on a 1-4 scale with 1 representing mild symptoms and 4, very severe symptoms. The instrument was designed as a clinical assessment form so

we will assess the psychometric properties of the Angina Log by comparing results to the SAQ-7 and the McGill Pain Questionnaire [®]. See **Table 1** for all variables, measures, and data collection time points.

c.7.1.f. **Massachusetts General Hospital Acupuncture Sensation Scale (MASS)**. The MASS Scale is a 13-item instrument which measures the intensity of sensations (on a 0-10 scale where 0 is no sensation felt by the patient and 10 is an unbearable sensation felt by the patient) when acupuncture needles are stationary or manipulated by the acupuncturist. This phenomenon called “*de qi*” is thought by many acupuncturists to be responsible for the therapeutic effect of acupuncture.⁷⁵

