Demographic Data	Demographic Data tionsForm	X		
Exploratory Aim				
Biomarkers	Interleukin 1 β , 2, 6, 8, 10 & 18; CRP, TNF- α	X		X
Outcome Measures				
Pain & Symptoms	McGill Pain Questionnaire; Seattle Angina Questionnaire-7; AHA Angina Log	X	X	X
Acupuncture Sensations	MASS		X	

Note: TX is treatment. s.d. is standard deviation. AHA is American Heart Association

c.9. Statistical Analysis. [name] will supervise data management and data analysis procedures. We will address missing data by intention to treat analyses (ITT), using the full information maximum likelihood (FIML) approach, which has been shown to produce unbiased parameter estimates and standard errors when data are missing at random⁸¹⁷⁷⁷⁶⁷⁶⁷⁶⁷⁶⁷⁶⁸³. All data will be exported from RedCap and imported into SAS version 9.4 for cleaning and analysis. All variables will be screened and descriptive statistics (frequencies, means,

standard deviations) will be used to describe the sample participants. Non-normal distributions may be optimally transformed using the Box-Cox method and/or analyzed using a comparable non-parametric test.

c.9.1. Aim 1: To determine the feasibility of study processes (recruitment, retention, completion, acceptability) to inform the design and execution of a future R21 study.

Hypothesis: Acupuncture therapy will be feasible (80% recruitment, retention, completion) and acceptable to individuals with chest pain or stable angina.

For the feasibility assessments descriptive statistics will be used for describing the subject characteristics and recruitment, retention & completion. We will explore patient characteristics that predict attrition and/or poor adherence to the treatment schedule. Data collected at every session will be explored to assess change in pain ratings following a session and if this pattern is consistent over the course of treatment. We are interested in knowing if pain and other symptom relief continues to improve linearly over the 5 weeks and 10 treatments or if a plateau is reached suggesting the need for fewer treatments.

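### The acceptability scale is scheduled only at 5 weeks with no rating at withdrawal, so early leavers are likely to go unscored, and the plan does not say whether controls count towards the criterion

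*Combined protocol and SAP*

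**What the plan says.** The Aim 1 hypothesis (c.9.1) is: "Acupuncture therapy will be feasible (80% recruitment, retention, completion) and acceptable to individuals with chest pain or stable angina". Section c.7.1.b describes the acceptability instrument as a "10-item instrument used to measure acceptability of the study processes and protocols" and adds: "Items are measured on a 0 (negative response, i.e. did not like acupuncture) to 2 (positive response) scale". High acceptability is a score above 10, which the same section labels as 80%.

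Table 1 names the "Protocol Acceptability Scale for Treating Angina with Acupuncture" and marks it once, in the 5-week column. The table is titled "Data Collection Variables, Measures, and Time Points (Both Groups" (closing bracket cut here). Section c.6.4 states: "Control group members will be offered the acupuncture protocol at study completion". At the 5-week rating, then, controls have watched videos and had no needling.

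No section describes a rating at withdrawal. None says who completes the scale, whose scores enter the criterion, or how withdrawals count. The c.9.1 sentence on descriptive analysis covers recruitment, retention and completion but does not mention acceptability. Section c.9 gives a general missing-data rule: intention to treat with full information maximum likelihood (FIML), justified for data missing at random.

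**The concern.** A participant who stops coming because needling was unpleasant holds the most informative view on acceptability, and the schedule has no point at which to collect it. If that group is unscored, the scale describes mainly those who stayed, and its mean is pushed upward.

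FIML does not repair this. The scale is given once, so someone who leaves has no earlier acceptability score to draw on, and a score missing because of dislike is not missing at random. Retention and completion count departures but do not record whether dislike caused them.

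The second gap is the analysis population. If control ratings were added to the criterion, part of the result would describe a video programme or an expectation, not experience of acupuncture. Aim 1 exists to inform the design of a later R21 study, so an acceptability figure from an undefined group is a weak basis for that design.

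**Working it through.** **The plan's own figure.** Ten items scored 0 to 2 give a maximum of 10 × 2 = 20. A score of 10 is 10/20 = 50%, and 80% of 20 is 16. The cut of more than 10 labelled 80% therefore does not reproduce. That is a separate defect. The written cut of more than 10 is used below, with 16 noted where it changes the reading.

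**Inputs from the protocol**
- Acupuncture arm 35, control arm up to 34 (c.6.1). Sections c.6.2, c.6.5 and c.8 use smaller totals, but the bias depends only on the fraction lost.
- Attrition of no more than 10% anticipated (c.6.3). Three of 35 is 8.6%.
- An 80% retention target (c.9.1), which tolerates up to 20% loss: 7 of 35.

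**Assumptions, with no source in the documents.** Completers average 17; drop-outs would have scored 4 to 8; the criterion is applied to the arm mean.

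**Formula.** All-participant mean = (completers × completer mean + drop-outs × drop-out mean)/35. Overstatement = completer mean − all-participant mean.

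| Lost | Drop-out score | All-participant mean | Overstatement |
|---|---|---|---|
| 3 | 8 | (32×17 + 3×8)/35 = 16.23 | 0.77 |
| 3 | 4 | (32×17 + 3×4)/35 = 15.89 | 1.11 |
| 7 | 8 | (28×17 + 7×8)/35 = 15.20 | 1.80 |
| 7 | 4 | (28×17 + 7×4)/35 = 14.40 | 2.60 |

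All four means exceed 10. Against 16, completers at 17 would pass, while three of the four all-participant means would not.

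**When the written cut could be affected.** Take the extreme case of drop-outs scoring 0 and a completer mean of 12. At 10% lost the mean is 12 × 0.9 = 10.8, still above 10. At 20% lost it is 12 × 0.8 = 9.6, below it. With 20% lost and drop-outs at 0, the break-even completer mean is 10/0.8 = 12.5.

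**If the arms were pooled.** Pooled mean = (35 × acupuncture mean + 34 × control mean)/69. With an acupuncture mean of 12, it runs from (420 + 0)/69 = 6.1 to (420 + 680)/69 = 15.9 as the control mean runs from 0 to 20. This shows only that the unstated choice of population can decide the result; nothing in the plan says that pooling is intended.

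**The case against.** A reader might infer that people who quit are never scored. The documents do not go that far. The Table 1 column is 5 weeks, not the end of session 10; stopping sessions is not the same as leaving the study; and c.6.3 collects several means of contact. A 5-week rating from someone who stopped needling is not excluded. It is simply not provided for.

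A reader might also infer that controls are scored on acupuncture. That rests only on the title of Table 1. The same table lists the MASS, which c.7.1.f says rates sensations "when acupuncture needles are stationary or manipulated by the acupuncturist" and which controls cannot answer, so the title is not literal for every row. The scale is also said to cover study processes, which controls can rate validly, and its items are in an appendix not in the available text. A statement that about half the scores (34 of 69) come from people without acupuncture is therefore not supported.

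Further, departures already count against the 80% retention and completion targets, and c.9.1 will explore predictors of attrition. The illustrative scores are assumed, and not every drop-out leaves from dislike. Section c.6.3 cites a prior 10-session trial with 36 accruals and no withdrawals, so 20% loss is about double what is expected.

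These points limit the size of the problem and the certainty with which it can be stated. They leave the gap in place: no rating is scheduled at withdrawal, and the respondents and analysis population are not defined.

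**Conclusion.** The point holds as a gap in timing and definition. As scheduled, the acceptability result will rest mainly on those who stayed and will tend to be biased upward, and the plan does not say whether controls count.

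Under the assumed scores, the bias is roughly 1 point on a 20-point scale at about the anticipated attrition and about 2 to 2.5 points at 20%. At the anticipated attrition, the written cut is unlikely to be crossed unless completers themselves score close to 10. Near 20% it could be crossed if completers average about 12 and drop-outs score very low. The direction is reasonably firm provided that some drop-outs leave from dislike; the size is illustrative. This is a cheap improvement, not a threat to the trial.

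**What to change.** In Table 1 and c.7.1.b:

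- Give the scale at 5 weeks or at withdrawal, whichever comes first, by phone or e-mail if the participant does not return.
- Apply the acceptability criterion to acupuncture-arm participants who had at least one session, and report how many of them were not rated.
- If controls complete the form, report their ratings of study processes separately and keep them out of the criterion.

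The cost is a few words in two places and a 10-item form at withdrawal, using contact details that c.6.3 already collects. The downside is that some people who withdraw will not answer, and the figure may be less favourable.
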